### *Patient centered outcome measures (n=131)*

Perceived quality of care and patient empowerment

Form based on PROMs (Patient Reported Outcome Measure) and PREMs (Patient Reported Experience Measure).

### *Quality-of-care outcome measures (n=131)*

Achieved target blood pressure, lipids, HbA1c

## Secondary outcome measures

### *Organ damage (n=131)*

Decline in eGFR.

### *System biology (n=260)*

Changes in markers of disease progression in transcriptomics, proteomics and metabolomics.

### *Health care structure and utilization (n=131)*

we will study the health care structure and function, involving cost effectiveness, both at HND-centrum and within usual care. Mixed model to describe health care utilization and explain changes in patterns. Number of outpatient and inpatient visits.

*Patient safety (n=131)*

Using logged patient safety reports.

*Interdisciplinary learning:*

Qualitative analysis of interdisciplinary learning between personnel.

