## Project plan

HND-centrum is an outpatient clinic that will replace visits to several doctors and nurses, where instead competence and care are organised and integrated around the patient.

The recently initiated study **Care-HND** (Fig. 2) will randomise 260 patients to HND-centrum or standard care.

The sample size is based on a power calculation for the combined outcome: death, readmission for heart failure, myocardial infarction, PCI/CABG, end stage renal failure or TIA / stroke with two years follow up.

The same power for quality of care and health care consumption require fewer patients, 131, to be randomized, and followed for 1 year.

**Figure 2.** Flowchart for the **Care-HND** study where 260 patients are randomised to HND-centrum or standard care. After one year's time crossover to the intervention arm is permitted. Intention-to-treat analysis.

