### **Integration with quality registries**

The majority of HND patients will continuously be registered in the national quality registries SWEDEHEART, National Diabetes Register and the Swedish Renal Registry. These in combination with National Welfare records on morbidity and mortality, and the Prescription Registry will be used for analysis of outcomes. Registry data will be used to characterize patients that meet the criteria HND but that are not randomised, in order to understand potential selection bias.

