**PhD Project 2: Value-based analysis of integrated clinic**

**- perceived quality of care and patient empowerment**

[name], [name], [name]. **PhD student [name].**

Study 1: Can **Care-HND** improve the patient's health-related quality of life?

Study 2: Can a multidisciplinary approach lead to a more involved patient?

Study 3: Can **Care-HND** fewer health care contacts in a patient safely?

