## **Research environment and Collaborators**

## **Clinical integration at Danderyd University Hospital**

HND-centrum is staffed by specialist doctors and specialist nurses in cardiology, endocrinology and nephrology, with a profound interest in the field, and share a common vision that we can do this better. All are deeply involved in the new clinic and are very positive about the planned CareHND study.

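### The only outcome labelled patient safety rests on logged reports, whose chance of being filed can depend on the randomised arm; between-arm counts cannot alone show that fewer contacts are safe

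*Protocol*

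**What the plan says.** Under Secondary outcome measures, the protocol lists "Patient safety (n=131)" and gives its source in one line: "Using logged patient safety reports". It gives no event definition, common reporting form, active collection or blinded review for this outcome.

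The Project plan states that the study "will randomise 260 patients to HND-centrum or standard care". It describes the intervention thus: "HND-centrum is an outpatient clinic that will replace visits to several doctors and nurses". For quality of care and health care consumption, the same section says that equal power would "require fewer patients, 131, to be randomized, and followed for 1 year".

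PhD Project 2, Study 3 asks whether the model can achieve "fewer health care contacts in a patient safely".

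Integration with quality registries names the quality registries and "National Welfare records on morbidity and mortality" as sources for outcomes in general, without tying them to patient safety. Disease progression, a primary outcome (n=260), includes death and readmission for acute renal failure, and inpatient visits are counted under Health care structure and utilization.

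**The concern.** A logged report exists only if an incident occurs, someone notices it, and someone chooses to file it. In most drug trials the same staff see both arms, so incomplete filing tends to affect both alike. Here randomisation decides which clinic treats the patient and hence, largely, which staff file the reports. The difference arises after allocation, so randomisation does not balance it.

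Two features make equal filing hard to take for granted. First, the intervention is intended to change the number of contacts at which an incident could be noticed and logged. Second, the protocol says of the HND-centrum staff: "All are deeply involved in the new clinic and are very positive about the planned CareHND study". That attitude could raise or lower reporting relative to usual care.

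At stake is the study question about fewer contacts delivered safely. If the log counts are read as the answer, a difference in filing could pass for a difference in safety, and a real difference in harm could be hidden.

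**Working it through.** The protocol gives no figure to reproduce: it states no incident rate, logging rate, alpha, effect size or contact rate for this outcome. The calculation shows how the bias works and how large it would be under assumed inputs.

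**Inputs**
- From the protocol: 131 patients; randomised factor is the place of care; one-year follow-up (stated for other n=131 outcomes, assumed to apply here).
- Assumed: an even split (66 and 65), two-sided 5% level, each patient counted as having a logged report or not, and all harm risks and logging probabilities.

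**Step 1. What a count measures.** For each arm, observed report risk = true harm risk × probability that the harm is logged. Hence

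observed ratio = (true harm ratio) × (logging ratio).

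With equal true harm the observed ratio is the logging ratio alone. If one setting logs 15% of incidents and the other 10%, it is 15/10 = 1.5; at 15% against 5% it is 15/5 = 3.0.

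**Step 2. Chance of a misleading significant result.** With p1 and p2 the observed report risks,

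P(significant) ≈ Φ[(|p1 − p2| − 1.96·SE0) / SE1],

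where SE0 uses the pooled proportion and SE1 the separate ones. Worked case: true risk 0.40 in both arms, logging 70% and 35%. Then p1 = 0.40 × 0.70 = 0.28 and p2 = 0.40 × 0.35 = 0.14. The pooled proportion is (66 × 0.28 + 65 × 0.14)/131 = 0.2105. SE0 = √[0.2105 × 0.7895 × (1/66 + 1/65)] = 0.0712. SE1 = √[0.28 × 0.72/66 + 0.14 × 0.86/65] = 0.0700. The argument of Φ is about 0.005, so the probability is about 0.50.

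The same formula over a range, with true harm equal in both arms throughout:

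| Logging, arm 1 vs arm 2 | Observed ratio | True risk 0.20 | True risk 0.40 | True risk 0.60 |
|---|---|---|---|---|
| 50% vs 50% | 1.0 | 5% | 5% | 5% |
| 60% vs 40% | 1.5 | 12% | 21% | 32% |
| 70% vs 35% | 2.0 | 25% | 50% | 74% |
| 80% vs 30% | 2.67 | 45% | 80% | 96% |

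The equal-logging row is the nominal level.

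**Step 3. Hidden harm.** Suppose true risk is 0.40 in one arm and 0.20 in the other, with logging of 35% and 70%. The observed risks are 0.40 × 0.35 = 0.14 and 0.20 × 0.70 = 0.14, a ratio of 1.0. With complete capture, the same doubling would have about 71% power at 66 and 65 patients.

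**Step 4. The role of contacts.** Suppose contacts are halved. If harm is unchanged and the chance of logging falls in proportion to contacts, the report ratio is 0.5 and is pure artefact. If incidents arise at contacts and logging per incident is unchanged, the ratio is also 0.5, but it is a real effect of the care model. The counts are identical in the two cases.

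**The case against.** Four objections deserve weight.

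*The harms that matter are already compared.* Death, acute renal failure readmission and inpatient visits are outcomes in their own right, and decline in eGFR is a secondary outcome. This stands. A reader might infer that the logs are the trial's only safety comparison; they are only the sole outcome carrying that label. The proposed events partly overlap the primary composite and the visit count.

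*No between-arm test of the logs is stated.* This also stands. A reader might infer that the trial plans to declare one model safer from these counts, but the protocol names a source and no more; Methods: Statistics and Data Management does not mention safety. How to count and model the reports may be left to a statistical analysis plan. The choice of source, however, is made in the protocol, and modelling cannot by itself make two unobserved filing rates equal. PhD Project 2, Study 3 asks a question that invites the comparison, although it does not say that these reports alone will answer it.

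*Unequal reporting is not shown.* Correct. The logging system is not described, and the arms might share one. It would therefore be too strong to say that the logs measure reporting habits instead of harm. They reflect both, mixed in unknown proportion.

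*Fewer contacts may mean fewer incidents.* Correct, as Step 4 shows, so a ratio of 0.5 cannot simply be called spurious. Nor are fewer contacts certain: the English abstract describes team visits and phone contacts as part of the intervention.

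**Conclusion.** The point holds in limited form. Because the protocol randomises the setting that delivers care and largely files the reports, the chance of logging can depend on the arm, and no safeguard is described. A between-arm reading of the counts cannot by itself support the claim that contacts were reduced safely.

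The direction and size of the bias are unknown. Under the assumed equal-harm scenarios with unequal logging, the observed ratio runs from 1.5 to 3.0 across Steps 1 and 2, and the chance of a misleading significant result from 12% to 96% in the table. Those figures rest on assumed risks and logging probabilities, an assumed even split and an assumed test, and are not estimates for this trial. What does not depend on them is that the observed ratio is the true ratio times the logging ratio, and that the logs cannot separate the two.

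This concerns one secondary outcome. The primary outcomes and the sample sizes are unaffected. The change is worth making because it is cheap.

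**What to change.** 1. Base the between-arm safety conclusion on a list of events fixed in advance and taken in the same way for both arms from the national records already planned: death, hospital admissions, admission for acute renal failure and other pre-listed complications. State where these overlap the primary composite and the inpatient visit count.
2. Report the logged incident reports by arm descriptively, alongside the number of contacts, with no between-arm test.
3. State in the protocol that the question about reducing contacts safely will not be answered from the logs alone.

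**Cost.** The record source is already planned, so little or no new collection should be needed. The protocol does not say in detail what the records hold, so it must be confirmed that they identify the listed events and cover both arms alike. Minor incidents and near misses that lead to no admission would be described but not formally compared. Admission is also not fully neutral, because the care model may influence whether a patient is admitted; the write-up should say so.

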**Methods: Cardiovascular structure and function**

Cardiac ultrasound, 24- hour blood pressure monitoring, sleep apnoea registration, thumb-ECG (AF screening) performed in clinical routine with validated equipment and structured interpretation. Arterial Stiffness measured using applanation tonometry and pulse-wave velocity. Endothelial function evaluated by forearm flow -mediated vasodilatation (FMD).

**Methods: PROM and PREM**

PROM (patient reported outcome Measures) stands for health-related quality of life, patient experience of care outcomes, measured by questionnaires EQ5 -D and RAND-36. PREM (patient- reported experience Measures) means that patients describe their experiences of care and can include measures of quality of life, experience, self-awareness and control. For PREM there are currently no standardised instruments, and we have developed a number of questions about the patient's experience.

**Methods: Statistics and Data Management**

Data are analyzed with statistics. Differences between groups in the time to outcome analyzed by log-rank test. Survival using Kaplan-Mayer. Hazard ratios with Cox proportional hazard model. Primary outcomes analysed according to the intention-to-treat principle.

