## Background – co morbidities and compound risk

The reasons why kidney failure causes heart disease, and vice versa (the cardiorenal syndrome) is still incompletely understood [9]. Patients with concomitant cardiovascular disease, renal dysfunction and diabetes are despite their high risk and high health care consumption often inadequately treated, since an increasingly specialised medical care too often focus on only one part of the disease panorama. Current studies and guidelines follow the same pattern.

In acute coronary syndromes, the single most common cause of death worldwide [2], approximately 40% of the patients have at least moderate kidney dysfunction with an eGFR below  $60 \text{ mL/min/m}^2$  [10]. The 1-year-mortality among these is about 25%, compared to 5% in patients with normal renal function [10]. The increased mortality in CKD patients after an acute coronary event is directly related to decreasing kidney function [4]. This may in part be due to the fact that patients with kidney dysfunction are receiving less active treatment, such

as early revascularisation [11], but may also be caused by a range of disturbances in for instance haemostasis and vascular function [3]. The lack of guidelines, which can be attributed to limited clinical data, as the majority of randomised trials in acute coronary syndromes so far have often excluded CKD patients [12].

More than 80% of all cardiovascular deaths can be delayed using changes in life-style and commonly prescribed drugs [13]. Despite this, many patients never receive the full benefits from these interventions because of frequent under-diagnosis, late presentation and consequent under-treatment [14,15]. This is particularly an issue for subjects with complex diseases such as concomitant cardiovascular disease, kidney dysfunction and diabetes.

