### Inclusion criteria – **Care-HND**:

- 1 - *Established cardiovascular disease* (history of myocardial infarction, angina, or heart failure requiring hospitalization. Previous stroke or TIA with certain diagnosis), as well as:
- 2 - *Diabetes mellitus type 1 or 2* (treated diabetes, or new onset diabetes according to WHO criteria or  $\text{HbA1C} > 48$ , and symptoms, as well as:
- 3 - *Established kidney disease* ( $\text{eGFR} < 60 \text{ mL/min/m}^2$  calculated with the CKD-EPI formula, or an average of the CKD -EPI and Cystatin-C eGFR, or borderline GFR but concomitant microalbuminuria, or macroalbuminuria, or kidney transplant).

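### The between-group test for the composite is a log-rank test with no strata or baseline covariates; it is valid but gives up some power that a pre-specified adjusted test would recover

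*Protocol*

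**What the plan says.** In the Protocol, section Methods: Statistics and Data Management, the comparison is assigned in one sentence: "Differences between groups in the time to outcome analyzed by log-rank test". Estimation follows separately: "Hazard ratios with Cox proportional hazard model". The analysis set is also fixed: "Primary outcomes analysed according to the intention-to-treat principle". No stratum or covariate is named, and none is ruled out.

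The Project plan section says the trial "will randomise 260 patients to HND-centrum or standard care", and that "The sample size is based on a power calculation for the combined outcome", with two years of follow-up. It states no significance level, power, effect size, event rate or allocation ratio.

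Two other sections bear on prognosis. The kidney criterion in the inclusion list takes eGFR below 60 with no lower limit, "or borderline GFR but concomitant microalbuminuria, or macroalbuminuria, or kidney transplant". The cardiovascular criterion covers angina, infarction, hospitalised heart failure, stroke and TIA. The background section on compound risk states: "The increased mortality in CKD patients after an acute coronary event is directly related to decreasing kidney function".

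**The concern.** A log-rank test can use baseline information only through strata, and none are named. When strong prognostic factors are left out of a time-to-event comparison, the expected unadjusted hazard ratio lies closer to 1 than the ratio conditional on those factors, and power falls.

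The eligibility criteria admit patients at quite different stages of kidney and heart disease. The composite contains death, heart failure readmission and renal failure, so baseline eGFR, age and previous heart failure hospitalisation are plausible predictors of it. With 260 patients and perhaps 60 to 105 events, this comparison has little power to spare. eGFR and cardiovascular history are already needed to decide eligibility, so adjusting for them asks for little new data.

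**Working it through.** **1. Inputs.** From the protocol: 260 patients, two years, log-rank test, intention to treat. Assumed because not stated: two-sided 5%, 1:1 allocation, no dropout, no crossover, two-year control risk 30–50%, exponential event times.

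**2. The plan's own figure.** The 260 cannot be reproduced, only back-solved. At 80% power the Schoenfeld formula gives d = 4(1.960 + 0.842)² / (ln HR)² = 31.4 / (ln HR)². Then N = d / mean(p₁, p₂), with p₂ = 1 − (1 − p₁)^HR.

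| Control risk p₁ | HR | Events d | p₂ | N |
|---|---|---|---|---|
| 30% | 0.48 | 59 | 15.7% | 259 |
| 40% | 0.54 | 83 | 24.1% | 259 |
| 50% | 0.58 | 106 | 33.1% | 256 |

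Many pairs fit, so 260 is neither confirmed nor refuted.

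**3. How large might the prognostic spread be?** The background gives one-year mortality of 25% with eGFR below 60 and 5% with normal renal function, in acute coronary syndromes. The implied hazard ratio is ln(0.75)/ln(0.95) = 0.2877/0.0513 = 5.6, or 1.72 on the log scale. A factor that strong, split 50:50, has a log-hazard SD of 1.72/2 = 0.86. That is an upper-end value for kidney function alone, because the trial largely excludes people with normal function. The range 0.5–1.0 used below is an assumption about all baseline factors together.

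**4. Ceiling: covariates capture the whole prognostic score.** Simulation with n = 260, 1,500 trials per cell and a conditional HR of 0.47–0.57, chosen for about 80% power without heterogeneity. Power is shown unadjusted → adjusted, with the gain in points.

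| Control risk | SD 0.5 | SD 0.8 | SD 1.0 |
|---|---|---|---|
| 30% | 79 → 80 (+1) | 74 → 81 (+7) | 69 → 82 (+13) |
| 40% | 77 → 80 (+3) | 74 → 83 (+9) | 68 → 82 (+14) |
| 50% | 79 → 83 (+4) | 69 → 82 (+13) | 66 → 84 (+18) |

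The simulation error of a single power is about √(0.8 × 0.2/1500) = 1 point.

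A second set (3,000 trials per cell) chose the HR so that the log-rank test itself had about 76–82% power:

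| Control risk, SD | Log-rank | Stratified log-rank | Adjusted Cox |
|---|---|---|---|
| 30%, 0.5 | 80 | 81 | 82 |
| 30%, 0.8 | 76 | 79 | 83 |
| 30%, 1.0 | 80 | 84 | 89 |
| 50%, 0.5 | 81 | 83 | 85 |
| 50%, 0.8 | 82 | 88 | 91 |
| 50%, 1.0 | 78 | 87 | 93 |

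The largest gain here is 15 points. For a single 50:50 factor with HR 5.6, stratified log-rank and adjusted Cox perform alike: 78 → 83 at 30% risk and 82 → 91 at 50%.

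**5. Realistic case: covariates capture part of the score.** In the nine cells of the first table, covariates explaining 25% of the prognostic variance gain about 1–3 points, and 50% gains about 2–7. At SD 1.0 with 50% explained, adjusted power is 72–75%. Repeating the simulation with another seed put the most extreme cell (50% risk, SD 1.0, half explained) nearer 9 points, so the top of the range is approximate.

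**6. Downside checks.** With a non-prognostic covariate (SD 0), Cox adjustment changes power by −0.5 to −1 point. Under no treatment effect (40% risk, SD 0.8), rejection rates were 4.8% for log-rank, 4.9% for stratified log-rank and 4.1% for adjusted Cox, so there is no inflation.

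**The case against.** The strongest reply is that nothing here is wrong. The log-rank test under intention to treat is valid, the protocol never calls its analysis unadjusted, and strata and covariates are commonly settled in a statistical analysis plan, which is not at hand. A stratified log-rank test is still a log-rank test, so such a plan could add strata without contradicting the protocol. All of that stands, and it makes this a point of efficiency only. What remains is that the protocol does choose a test, gives the comparison to log-rank and names no strata. Moving the primary inference to an adjusted Cox model would change that text.

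Some stronger readings are tempting, but the document does not support them:

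- *The Cox model has no covariates.* The text is silent on this.
- *Risk in this trial spans 25% against 5%.* That contrast is mortality in acute coronary syndrome patients, set against a normal-function group the trial largely excludes, while the endpoint is a broader composite. The stated gradient with falling kidney function is better support, but it is qualitative and follows an acute coronary event, so it is indicative only.
- *Adjustment would hold power at 80–84%.* This needs covariates that capture the whole prognostic score.
- *The unadjusted hazard ratio is biased.* At 40% risk and SD 0.8 it moves from 0.53 to about 0.56. That is the difference between a marginal and a conditional hazard ratio, not a bias.
- *260 is too few for this reason.* If 260 was derived from marginal event rates, the log-rank power is already the planned power.

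**Conclusion.** The point holds as a moderate efficiency improvement to a valid test. On assumed inputs (260 patients, control risk 30–50%, prognostic SD 0.5–1.0), the likely gain is about 1–7 points of power with covariates that explain 25–50% of the prognostic variance. It reaches about 15 points or slightly more (18 in the most favourable cell) only with nearly complete capture, and it is small at SD 0.5 however good the covariates. The direction does not depend on these inputs as long as the covariates are prognostic; the size does, and the protocol offers nothing to narrow it. Calling the gain free would also go too far, though the cost is small. Crossover of controls after one of the two years is a separate threat to power that baseline adjustment does not address.

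**What to change.** In Methods: Statistics and Data Management, replace the log-rank sentence with one of two options for the primary test of the composite:

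- a Cox model with treatment and a few baseline covariates fixed before any outcome data are seen, for example eGFR, age and previous heart failure hospitalisation; or
- a log-rank test stratified by baseline eGFR category, with the categories defined in advance.

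Keep the unstratified log-rank test and the Kaplan-Meier curves as supportive. The first option usually recovers more when the risk gradient is continuous; the second stays closer to the present wording.

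Cost: one or two sentences. The covariates must be specified in advance and measured at baseline for every patient. The Cox-adjusted hazard ratio is conditional on them and should be reported as such. A covariate that turns out not to be prognostic gains nothing.
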